Regular use of intranasal corticosteroid (such as intranasal Fluticasone propionate 400 μ g per pipette; $\frac{1}{2}$ pipette 1-2 x /day to both nostrils or intranasal corticosteroid spray 1 dose 1-2 x /day to both nostrils if patient is not able to use the drops) is started at least 2 months prior to study entry. Regular CRSwNP and asthma medication is used throughout the whole study.

Exclusion criteria:

- Age <18 years
- CRS-surgery < 6 months before 1st visit
- pregnancy/ breastfeeding. FRPs need to perform pregnancy test prior to the CT/CBCT scans. If subject is already on contraception prior to the study this should be continued.
- complication of CRS (f.ex. mucocoele, invasive fungal rhinosinusitis). Take sinus CT/CBCT scans, if needed!
- acute rhinosinusitis/respiratory infection
- severe disease related to airways/ immunology: cystic fibrosis, primary ciliary dyskinesia (PCD), sarcoidosis, immunosuppression, diagnosed Specific antibody deficiency (SAD), CVI, HIV, fungal rhinosinusitis; Young syndrome; Kartagener syndrome;
- other severe disease such as active cancer
- Received biologic therapy/systemic immunosuppressant/ASA desensitization therapy/experimental monoclonal antibody treatment to treat inflammatory or autoimmune disease within 2 months of study entry or 5 half-lives, whichever is longer. The patient is allowed to use ASA dose <100 mg/day due to cardiovascular reasons after ASA desensitization.
- current immunotherapy
- communication problems (f.ge. neurological/psychiatric disease, language skills)
- unlikely to comply
- ASA-challenge negative.
- History of hypersensitivity to mepolizumab or excipients in the formulation

Power calculation: The mean postoperative difference in the Sinonasal Outcome test (SNOT-22) was assumed to be at least 9 between the treatment arms. In a previous study the response within each subject group was normally distributed with standard deviation 17. If the true difference in the experimental and control means is 13, we will need to study 57 experimental subjects and 57 control subjects to be able to reject the null hypothesis that the population means of the experimental and control groups are equal with probability (power) 0.8. The Type I error probability associated with this test of this null hypothesis is 0.05. The total number recruited is 120 (estimated rate of discontinuation is 5%).

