The statistical analyses will be conducted in the modified intention-to-treat (mITT) population, defined as all randomized participants who received at least one dose of the investigational medicinal product and fulfilled the inclusion criteria. One randomized participant was excluded due to failure to meet inclusion criteria, resulting in 47 participants per treatment group. All analyses were performed blinded to treatment allocation, and the randomization code was opened only after the trial was closed and the primary analyses completed. The sample size was calculated to provide 80% power to detect clinically meaningful differences in the coprimary endpoints using a two-sided significance level of 0.05. Baseline was defined as the recruitment visit, occurring approximately eight weeks prior to initiation of the investigational medicinal product. Participants received four injections over a 16-week treatment period, followed by an additional eight-week observation period without treatment, after which final measurements were obtained. Continuous variables are summarized using means with standard deviations or medians with interquartile ranges, as appropriate, and categorical variables using frequencies and percentages. The coprimary endpoints and all secondary continuous outcomes were analyzed as changes from baseline using linear mixed-effects models. These models included fixed effects for treatment group, time, and their interaction, and a random intercept for participants to account for within-subject correlation over repeated measurements. Group-specific changes from baseline were estimated at each follow-up time point, and treatment effects were assessed by comparing differences in these estimated changes between groups. Results are reported as mean differences with 95% confidence intervals. A two-sided significance level of $p < 0.05$ was applied to all analyses, and no formal adjustment for multiple comparisons was performed. Model assumptions were evaluated by visual inspection of residual plots to assess normality and homoscedasticity, and by examination of fitted values and influence diagnostics to identify outliers or model instability. The linear mixed-effects modeling framework was selected because it accommodates unequally spaced measurements and missing observations and provides unbiased estimates under the missing-at-random assumption.

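### The protocol ties 57 patients per arm to a SNOT-22 difference of 13, but 57 is the answer for 9; the SAP does not restate power for the 47 per arm analysed or show the basis for the polyp score

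*Protocol*

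**What the plan says.** The power calculation in Protocol section 2.1 opens with one difference: "The mean postoperative difference in the Sinonasal Outcome test (SNOT-22) was assumed to be at least 9 between the treatment arms". It then takes from a previous study that "the response within each subject group was normally distributed with standard deviation 17". The next sentence uses a second difference: "If the true difference in the experimental and control means is 13, we will need to study 57 experimental subjects and 57 control subjects", for power 0.8. On the error rate it says only that "The Type I error probability associated with this test of this null hypothesis is 0.05", without stating one- or two-sided. Recruitment is set at 120 to allow for 5% discontinuation.

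The SAP, which has no numbered sections, states: "The sample size was calculated to provide 80% power to detect clinically meaningful differences in the coprimary endpoints", at a two-sided 0.05 level. It names the coprimary outcomes as the Nasal Polyp Score and the SNOT-22 total score. It reports one exclusion, "resulting in 47 participants per treatment group". The planned analysis is a linear mixed model on change from baseline with a random intercept. The SAP sentence on power gives no difference or SD for either endpoint.

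**The concern.** One power statement cannot rest on two different target differences. If 13 is the design value, 57 per arm is about twice what the stated inputs require. If 9 is the design value, the sentence that justifies the sample size is wrong.

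The choice matters because the analysed size is smaller than planned: 94 patients against 114 planned evaluable. A reader who takes 13 at face value would regard a non-significant SNOT-22 result as strong evidence against a worthwhile effect. A reader who takes 9 would see a comparison that fell short of its intended power.

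The SAP also extends the 80% claim to the polyp score, while the calculation in the protocol concerns SNOT-22 alone. The word postoperative adds to the doubt about where the inputs came from, because the randomised comparison is mepolizumab against placebo injections.

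**Working it through.** **Inputs.** SD 17, power 0.80, alpha 0.05, differences 9 and 13, 57 per arm, 5% discontinuation and 120 recruited (all Protocol section 2.1); 1:1 allocation (Protocol section 1); two-sided testing and 47 analysed per arm (SAP).

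**Step 1: size per arm.** By the normal approximation, n = 2 × SD² × (1.960 + 0.8416)² / d² = 2 × 289 × 7.849 / d² = 4,537 / d².

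- d = 13: 4,537 / 169 = 26.8, so 27 per arm. The exact t calculation gives 28.
- d = 9: 4,537 / 81 = 56.01, so 57 per arm. The exact t calculation gives 56.98, also 57.

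The plan's figure of 57 is reproduced by 9 and not by 13.

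**Step 2: recruitment total.** 2 × 57 = 114, and 114 / (1 − 0.05) = 120. This matches the protocol, so the recruitment target also follows from 9.

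**Step 3: can 13 be rescued?**

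| Variant for d = 13 | Per arm |
|---|---|
| One-sided 0.05, power 0.80 | 22 |
| Two-sided 0.05, power 0.80, Mann-Whitney efficiency 0.955 to 0.864 | about 29 to 32 |
| Change-score SD of 17 × √2 = 24.0 (zero correlation) | 54 to 55 |
| One-sided 0.05, power 0.99 | 54 to 55 |

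The last two come close to 57, but one departs from the stated SD and the other from the stated power. For 57 per arm to give 80% power at 13, the SD would have to be about 24.6 (exact t).

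**Step 4: power by size** (two-sample t test, SD 17, two-sided 0.05).

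| Per arm | Power at 9 | Power at 13 |
|---|---|---|
| 57 (planned) | 80.0% | 98.2% |
| 47 (analysed) | 71.9% | 95.6% |

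Normal check at 47 per arm and d = 9: the standard error is 17 × √(2/47) = 3.51; 9 / 3.51 − 1.96 = 0.61, which gives about 73%.

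**Step 5: detectable difference at 47 per arm.** By the normal formula, 2.8016 × 3.51 = 9.8. The exact t value is 9.9 points.

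**Step 6: dependence on the SD.** The mixed model may have an effective SD other than 17. At 47 per arm and d = 9, power is 82.1% for SD 15, 77.0% for SD 16, 66.9% for SD 18 and 57.9% for SD 20. It reaches 80% at an SD of about 15.4.

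**Polyp score.** No difference or SD is given in the visible text, so its power cannot be computed in either direction.

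**The case against.** The strongest reply is that 13 is a drafting slip with no effect on the trial's size: 57 and 120 are both right for the 9 stated in the same paragraph. That stands. It limits the consequence, but the sentence justifying the size is still wrong.

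The SAP sentence describes the planned calculation and does not claim that 47 per arm has 80% power. That also stands. The gap is that a smaller analysed size is reported beside the planned figure with no restated power.

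The 72% rests on an unadjusted t test, while the SAP uses a mixed model. This stands as a condition on the figure; nothing in the documents shows that the effective SD is 15.4 or less. Results are also to be reported with 95% confidence intervals, so readers can judge precision directly. That softens the harm but does not correct the stated basis.

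Three stronger readings are not supported:

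- A reader might infer that 80% power is missed for both coprimary endpoints. This cannot be shown for the polyp score, because its inputs are not visible.
- A reader might infer that the polyp score was never powered. Part of the SAP was not available for this review, and the visible part claims power for the coprimary endpoints together. The claim is unsupported in the visible text, which is not the same as false.
- A reader might quote a joint power for success on both endpoints. That needs an assumed polyp-score power and a rule that both must succeed. The visible text gives neither.

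**Conclusion.** The protocol sentence is wrong as written. Under its own SD, power and alpha (taken as two-sided, from the SAP), 57 per arm belongs to a SNOT-22 difference of 9; 13 would need 28. The recruitment total of 120 also fits 9, so the error lies in the stated difference and not in the number planned.

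With 9 as the design difference, the 47 per arm analysed give about 72% power, and the difference detectable with 80% power is about 9.9 points. Both figures assume an unadjusted t test with SD 17. If 13 were meant, power at 47 per arm would be 95.6%, which is why the two figures must be reconciled before a SNOT-22 result is interpreted.

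For the nasal polyp score, the finding is limited to this: the 80% claim has no visible basis, and the SAP does not say whether 80% applies to each endpoint or to both jointly.

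**What to change.** **Protocol, power calculation.** Change the sentence to read: true difference 9, SD 17, 57 per arm, 80% power, two-sided 0.05. Remove or explain the word postoperative, since the arms differ by injection and not by surgery.

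**SAP, beside the planned 80% statement.** Add text such as: *The planned size for SNOT-22 was 57 per arm (difference 9, SD 17). With 47 per arm analysed, power for a 9-point difference is about 72%, and the difference detectable with 80% power is about 9.9 points (unadjusted t test, SD 17). The mixed model would regain 80% at 9 points only if its effective SD were about 15.4 or less.*

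**SAP, polyp score.** State the difference and SD behind the 80% claim and whether it is per endpoint or joint. If no such calculation exists, limit the claim to SNOT-22.

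The cost is wording only. No extra patients or analyses are needed, and the stated power becomes less favourable.

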- Lund Mackay score ≥ 12 (maximum 24) of sinus computed tomography (CT) or cone beam (CBCT) scans. The new sinus CT/CBCT scans are needed if the previous sinus CT/CBCT scans have been performed over 36 months before recruitment visit and it is clinically indicated, or if there is a suspicion of complication of CRS (f.ex. mucocoele, invasive fungal rhinosinusitis). Pregnant and breast-feeding subject will be excluded. Females of Reproductive Potential (FRPs) who are not pregnant or breast-feeding may be enrolled. FRPs need to perform pregnancy test prior to the CT/CBCT scans. If subject is already on contraception prior to the study this should be continued. The data of previous sinus CT/CBCT scans will be used if previous sinus CT/CBCT scans have been performed ≤ 36 months prior to recruitment visit. The clinical information of sinus CT/CBCT scans is critical to enrolling appropriate subjects for the research and cannot readily be obtained another way. The radiation dose of sinus CT/CBCT scans is less than 0.1 mSv, which corresponds to less than 10 days of natural background radiation in Finland. The increased cancer risk is minimal.
- ≥ 1 previous CRS-surgery. Note that the last CRS-surgery must have been performed at least 6 months before 1st visit
- SNOT-22 ≥ 25
- At least one other symptom, such as partial loss of smell (hyposmia), nasal obstruction, total loss of smell (anosmia), or anterior or posterior rhinorrhea
- patient should have a history of at least one exacerbation during the past two years e.g. at least one criterion must be fulfilled of the following list during the past two years ≥ 1 oral corticosteroids; ≥ 3 antibiotic courses; ≥ 1 CRS-operation; ≥ 1 asthma hospitalization. In patients with contraindications of previously listed treatment or continuous oral steroids, additional criteria are not required.
- Asthma diagnosis (patient has the National Social Insurance Institution's reimbursement right for asthma medication)
- Peripheral blood eosinophils (PBEos) > 300 cells/ μ l at visit 1 OR (PBEos > 150 cells/ μ l at visit 1 AND a history of PBEos > 300 cells/ μ l during the past 12 months). A history of Nasal polyp tissue eosinophilia (NPeos) $\geq 30\%$ during the past 12 months is a supportive criterion.

The two treatment arms, s.c. Mepolizumab and s.c. placebo injections are randomized in a ratio of 1:1 of the study patients and is scheduled 2-4 weeks before start of trial medication.

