ASA challenge is conducted during the second visit if needed, according to modified international protocol (15-16). FEV1 should be at least 1.5 L and > 60% of predicted before challenge or desensitization. Patient will receive 25 mg ASA at a hospital setting. If no remarkable symptoms are seen, patient will receive 1-2 hours later another 25 mg ASA at a hospital setting.

ASA challenge positive result:

1. Naso-ocular alone: a 30 % or > increase in at least one of the following VAS (0-10 cm) scores: nasal obstruction, nasal discharge, postnasal drip, eye itching. These may exist with or without objective signs of increased nasal turbinate swelling/discharge or eye redness in examination.
2. Naso-ocular (please see 1.) and a 15% or > decline in FEV1 or in PEF (Classic reaction)
3. Lower respiratory reaction only (FEV1 or PEF declines by >20%)
4. Laryngospasm with or without 1-3 (flat or notched inspiratory curve)
5. Systemic reaction: hives, flush, gastric pain, hypotension

Patients Randomization and the treatment arms I-II occurs after 1st (or 2nd for ASA challenged) visit. The patients are randomized to two treatment arms: I) subcutaneous injections of placebo once per month for 16 weeks II) subcutaneous injections of Mepolizumab once per month for 16 weeks. Mepolizumab 100 mg / Placebo (NaCl solution)

is injected subcutaneously once per month, for a total of 16 weeks. GSK provides the randomization codes to each center.

Table1 the study protocol

| Time | -4 weeks | -2 weeks | 0 weeks | 4 weeks | 8 weeks | 12 weeks | 16 weeks | 20 weeks |
|--|---------------|----------------------|----------------|----------------|----------------|----------------|-----------------|--------------|
| Visit | 1 | 2 | 3 | 4 | 5 | 6 | 7 | 8 |
| | Rekrytointi | ASA-aslustus | 1. pistoskerta | 2. pistoskerta | 3. pistoskerta | 4. pistoskerta | Seurantakäynti | Loppukäynti |
| Name of the visit | Recruitment | ASA-challenge | 1st injection | 2nd injection | 3rd injection | 4th injection | Follow-up visit | End of Trial |
| Informed Consent | x | | | | | | | |
| Review Inclusion / Exclusion Criteria | x | x No flu 2 we before | x | | | | | |
| Medical History comorbidities | x | | | | | | | |
| Randomization | x | x | | | | | | |
| Visiting Doctor | x | x | x | x | x | x | x | x |
| Visiting Nurse | x | x | x | x | x | x | x | x |
| Review of Concomitant Medication | x | x | x | x | x | x | x | x |

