| Visits, hospitalisations, exacerbations, sick leave, productivity | Previous year | | | | | | | |
| Allergy test = serum specific IgE test (pölyerittely) | x | | | | | | | |
| | x | | | | | | x | |
| ASA challenge test (to subjects without previous challenge-test-confirmed NERD dg) | | x | | | | | | |
| Treatment with IMP | | | x | x | x | x | | |
| Check side-effects | | x | x | x | x | x | x | x |
| ENT visit (+ lung examination) | x | x | x | x | x | x | x | x |
| Check CRS control | x | x | x | x | x | x | x | x |
| Pulmonologist visit | x | | | | | | x | |
| Check asthma control | x | x | x | x | x | x | x | x |
| Questionnaire-packet: SNOT-22, 15D, AQLQ, Asthma control | x | x | x | x | x | x | x | x |

| | | | | | | | | |
|---|---|----|---|---|---|---|---|-------------------|
| test, 2xNetherlands-Q | | | | | | | | |
| VAS symptoms | | x | | | | | | |
| Baseline characters questionnaire (esitietokaavake) | x | | | | | | | (x) if changed |
| Acoustic rhinometry (ARM) | x | xx | x | x | x | x | x | x |
| nNO | x | xx | | | | | x | |
| eNO | x | | | | | | x | |
| Olfaction Sniffin' sticks | x | | x | x | x | x | x | x |
| sinus CT scans | x | | | | | | | |
| Blood analysis for Biobank | x | | | - | - | - | | - |
| Blood samples (5 EDTA tubes) for metabolomics & genomics | x | xx | x | x | x | x | x | x |
| Urine samples for metabolomics | x | xx | x | x | x | x | x | x |
| Fecal sample for microbiome | x | | x | x | x | x | x | x |
| Nasal samples (microbiome, transcriptomics, histology) | x | xx | | | | | x | |
| Spirometry | x | | | | | | x | |
| PEF 1 week | x | x | | | | | x | |
| microspirometry | | x | | | | | | |
| PEF at visit | x | x | x | x | x | x | x | x |
| PNIF at visit | x | x | x | x | x | x | x | x |
| Check disease relapse | x | x | x | x | x | x | x | x |
| Consider additional therapy /referral to operation | x | x | x | x | x | x | x | x |

Study endpoints

Primary, Change from baseline

endoscopic nasal polyp score (total score ranges between 0-8 of both sides), SNOT22 symptom score, VAS score (of smell loss, obstruction, postnasal drip, nasal discharge, facial pain/pressure) and, exacerbation-rate. Exacerbation means that patient has at least one of the following due to airway symptoms: oral corticosteroid course; antibiotic courses; sinus lavation; hospitalization.

Secondary, Change from baseline

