No imputation methods were applied for missing data. To assess the robustness of the findings and the plausibility of the missing-at-random assumption, sensitivity analyses were performed. These included a complete-case analysis restricted to participants with available data at all time points and an analysis excluding participants who received systemic oral corticosteroids

for exacerbations at any point during the trial. The corticosteroid exclusion analysis evaluated the coprimary outcomes (Nasal Polyp Score and SNOT-22 total score) as well as lung function outcomes, including relative changes in peak nasal inspiratory flow, peak expiratory flow, forced expiratory volume in one second, and corresponding microspirometry measures. Sensitivity analyses were conducted in the per-protocol population on an available-case basis using the same statistical models, confidence intervals, and significance thresholds as the primary analyses. Consistency of results across analyses was used to support the validity of the primary findings. All statistical analyses were performed using R statistical software, version 4.5.1.

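### Two of the protocol's four primary endpoints are left without a workable analysis: symptom VAS has no scheduled post-treatment value, exacerbation rate has no like-for-like baseline or rate model, and the available SAP text names only the other two, without explanation

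*Protocol*

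**What the plan says.** **Protocol, Study endpoints.** The primary list is headed as change from baseline. It opens with "endoscopic nasal polyp score (total score ranges between 0-8 of both sides), SNOT22 symptom score, VAS score" and continues: "VAS score (of smell loss, obstruction, postnasal drip, nasal discharge, facial pain/pressure) and, exacerbation-rate". That makes four endpoints, with VAS covering five symptoms. An exacerbation is defined by any one of four airway-related events: an oral steroid course, antibiotic courses, sinus lavage or hospitalisation.

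**Protocol, Table 1.** The VAS row reads "VAS symptoms | | x" and is blank from visit 3 on. The single mark is at visit 2, two weeks before the first injection. Section 2.1 says "ASA challenge is conducted during the second visit if needed", so not every participant need have that visit. The row naming exacerbations reads "Visits, hospitalisations, exacerbations, sick leave, productivity | Previous year" and has no on-study mark. Concomitant medication and disease relapse are each marked at all eight visits.

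**Protocol, Statistics.** Exacerbations are listed among the variables to be analysed. The named methods are t, Mann-Whitney, Kruskal-Wallis, chi-square and Fisher tests, and linear and logistic regression. None is a rate model.

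**SAP.** The sensitivity-analysis paragraph identifies the "coprimary outcomes (Nasal Polyp Score and SNOT-22 total score"). The analysis paragraph applies linear mixed models to the change from baseline in the coprimary and continuous secondary outcomes. VAS is not mentioned. Exacerbations appear only as the reason for oral steroids, in a sensitivity analysis that removes the participants who received them. The opening part of the SAP was not available.

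**The concern.** The protocol's Summary puts reducing exacerbations in the trial's aim, beside polyp size and SNOT-22. If the plan is followed as written, two endpoints that the protocol calls primary get no analysis: one has no scheduled follow-up value, and the other has no usable baseline contrast and no model.

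The timing adds to this. The SAP already reports 47 participants per group. When a primary set shrinks from four to two in a document that knows the analysed numbers, readers will ask whether the choice was made before or after results were seen. The available text gives neither a date nor a reason that would answer them.

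**Working it through.** **1. What the plan's own calculation covers.** The only sample size is for SNOT-22. With SD 17, difference 9, two-sided alpha 0.05 and power 0.80, n = 2 × (1.960 + 0.842)² × 17² / 9² = 56.01, rounded up to 57 per arm. This reproduces the stated 57, and 114 / 0.95 = 120. (The power paragraph also states a difference of 13, which would give 27. That is a separate matter.) No rate, dispersion or exposure is given for exacerbations and no difference for VAS, so no planned power for either can be checked.

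**2. VAS against the schedule.**
- Visits marked: 1 of 8. Visits marked after treatment starts: 0.
- The questionnaire packet, marked at all eight visits, lists SNOT-22, 15D, AQLQ, the asthma control test and two Netherlands questionnaires, but not VAS.
- The VAS use described in section 2.1 belongs to the challenge. A positive naso-ocular result is a rise of at least 30%, an "increase in at least one of the following VAS (0-10 cm) scores: nasal obstruction, nasal discharge, postnasal drip, eye itching". Those items omit smell loss and facial pain or pressure, two of the five endpoint symptoms.

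The single mark therefore fits the challenge and not the endpoint. The schedule provides no pair of values from which a change could be formed.

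**3. Exacerbation windows.**
- History: 52 weeks.
- On trial, protocol Table 1 (first injection to end of trial): 20 weeks, 20/52 = 0.38 of a year.
- On trial, SAP read literally (16 weeks of treatment plus 8 of observation): 24 weeks, 24/52 = 0.46 of a year.

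A participant with a constant rate of one event per year would be expected to show 1 event in the history and 0.38 in 20 weeks. That is a fall of 62% in the raw count with no treatment effect. Annualising does not rescue the measure: each on-trial event becomes 52/20 = 2.6 per year, so a participant can score only 0, 2.6, 5.2 and so on. Entry also requires a history of exacerbation or related treatment for most participants, so some fall is expected from regression to the mean.

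Both arms share these features, so a between-arm comparison of changes is not biased by them. The within-arm change cannot be interpreted, however, and subtracting a recalled count adds noise. The on-trial count, with history as a covariate, avoids both problems.

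**4. Precision of an on-trial comparison.** Assumptions, none from the documents: placebo rate 1 to 2 per year, rate ratio (RR) 0.5 to 0.6, negative binomial dispersion k from 0.5 to 1. From the SAP: 47 per arm and two-sided 0.05. With μ = rate × weeks/52,

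Var(log RR) = (1/μ₀ + 1/μ₁ + 2k) / 47, and power = Φ(|ln RR| / SE − 1.960).

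| Weeks | Rate, RR, k | μ₀, μ₁ | Var | SE | Power |
|---|---|---|---|---|---|
| 20 | 1, 0.6, 1 | 0.385, 0.231 | 8.933/47 = 0.190 | 0.436 | Φ(−0.788) = 0.22 |
| 20 | 2, 0.5, 0.5 | 0.769, 0.385 | 4.900/47 = 0.104 | 0.323 | Φ(0.187) = 0.57 |
| 24 | 1, 0.6, 1 | 0.462, 0.277 | 7.778/47 = 0.165 | 0.407 | Φ(−0.704) = 0.24 |
| 24 | 2, 0.5, 0.5 | 0.923, 0.462 | 4.250/47 = 0.090 | 0.301 | Φ(0.345) = 0.635 |

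In the least favourable 20-week case, about 47 × 0.385 = 18 events are expected on placebo and 47 × 0.231 = 11 on mepolizumab.

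**The case against.** **On-trial exacerbations can be captured.** A reader might infer that the exacerbation endpoint cannot be produced at all, or that the trial cannot address exacerbations. The documents do not support that. Medication and relapse are checked at every visit, the section on adverse events has all contacts with the study unit entered in the eCRF, and medication for exacerbations is a secondary endpoint. The SAP itself identifies participants given oral steroids for exacerbations. The protocol's general tests could also be applied. This stands. The defect is narrower: no stated window, denominator, rule for separating episodes or rate model.

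**Table 1 does not record everything collected.** Microspirometry is likewise marked only at visit 2, yet the SAP analyses relative changes in it. Polyp score has no row of its own, yet it is coprimary. So the VAS row shows a gap in the schedule. It does not show that VAS was never collected. This stands too.

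**The two coprimaries have roots in the protocol, and analysis was blinded.** The first research question in section 2.1 concerns polyp score and SNOT-22; exacerbation rate comes in the second. The SAP says that the code was opened only after the primary analyses were complete. Selective reporting is therefore not shown. Both facts would help the sponsor more if the change were dated and explained. The placing in section 2.1 also conflicts with the endpoint list and needs reconciling.

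**The SAP text is incomplete here.** A reason may be given in the part that was not available. That limits the claim to the text seen, although that text names the two coprimaries explicitly.

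**The eligibility list is not evidence of a mismatch.** The entry criterion "≥ 1 oral corticosteroids; ≥ 3 antibiotic courses; ≥ 1 CRS-operation; ≥ 1 asthma hospitalization" differs from the endpoint definition, and a reader might count that as a further inconsistency. It is a two-year entry rule and not the endpoint's baseline, so it need not match.

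**Conclusion.** The point holds in limited form. From the schedule as written, no participant has a planned post-treatment VAS, so that primary endpoint cannot be formed. Exacerbation rate as a change from baseline sets 52 recalled weeks against 20 or 24 on trial (38% or 46% of a year) and should be replaced by a between-arm comparison of on-trial counts. The available SAP text reduces four primaries to two without a reason or a date and contains no rate or count analysis.

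This is a gap in planning and disclosure. It does not establish that VAS data are absent, that exacerbation data are lost, or that endpoints were chosen after results were known. The schedule and endpoint findings are read directly from the documents and need no assumptions. Only the power range does (about 0.22 to 0.57 at 20 weeks, 0.24 to 0.635 at 24), and it serves only to warn that a null exacerbation result would be weak evidence of no effect.

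**What to change.** 1. **Disclose the change.** State in the SAP that the primary set went from four endpoints to two, the date of that decision relative to opening the randomisation code, and the reason. Reconcile the research questions in section 2.1 with the endpoint list. Cost: a few sentences.

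2. **Settle VAS.** State whether the five-symptom VAS was recorded after baseline. If it was, report it by arm. If it was not, remove it from the primary list and say so. Cost: one check of the eCRF.

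3. **Analyse exacerbations on trial.** Derive each participant's count from first injection to end of follow-up, using the protocol's definition and a written rule for when overlapping courses count as one episode. State whether follow-up ends at week 20 or 24. Compare arms by negative binomial regression with log follow-up time as offset, adjusted for previous-year count and centre, in place of change from baseline. Report the rate ratio with its 95% interval whatever the result, and note that the trial was not sized for it. People unaware of allocation should do the abstraction.

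The third item costs some record abstraction and one model. Extra visits are not an option in a trial whose analysed numbers are already reported. The drawback is low precision: in the least favourable 20-week case the 95% interval would extend by a factor of exp(1.96 × 0.436) = 2.35 either side of the estimate.
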